#### 5.3.6 Study Medication Dose Calculation

The number of capsules of study drug to be administered will be the same for all the subjects enrolled to the same dosing cohort. Two 20-mg capsules per dose will be administered to subjects at Dose Level 1, four 20-mg capsules per dose will be

administered to subjects at Dose Level 2, five 20-mg capsules per dose will be administered to subjects at Dose Level 3 and 4, six 20-mg capsules per dose will be administered to subjects at Dose Level 5, eight 20-mg capsules per dose will be administered to subjects at Dose Level 6, and ten 20-mg capsules per dose will be administered to subjects at Dose Level 7.

Analyses of PK data do not reveal an advantage for body-weight-based dosing in minimizing variations of PTC299 plasma exposure. Using a fixed dosing regimen offers convenience for pharmacies in dispensing the drug and helps to ensure subject compliance in drug administration. To date, six cancer patients have received 0.3 mg/kg/dose of PTC299 BID and six cancer patients have received 0.6 mg/kg/dose of PTC299 BID for at least 4 weeks. PTC299 has been generally well tolerated. No PTC299-related AEs or dose-limiting toxicities have been reported. A preliminary PK analysis suggests that the target plasma concentration of ~0.15 µg/mL is readily achievable with the planned dose levels.

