### 5.3.2 Dose Escalation Rules and Definition of MTD

In Stage 1, each subject will be assigned to Dose Level 1 (40 mg/dose BID), Dose Level 2 (80 mg/dose BID), or Dose Level 3 (100 mg/dose BID) sequentially according to the dose level being explored at the time of subject enrollment. A Dose Level -1 (20 mg/dose BID) is provided in case a subject assigned to Dose Level 1 (40 mg/dose BID) requires dose reduction. In Stage 2, 8 subjects were enrolled at the Stage 1 MTD, Dose Level 2 (100 mg/dose BID). In Stage 3, each subject will be assigned to Dose Level 6 (160 mg/dose TID), or Dose Level 7 (200 mg/dose TID) sequentially according to the dose level being explored at the time of subject enrollment. Dose Level 5 (120 mg/dose TID) is provided in case a subject assigned to Dose Level 6 (160 mg/dose TID) requires dose reduction. Dose Level 4 (100 mg/dose BID) is provided in case a subject assigned to dose Level 5 (120 mg/dose TID) requires dose reduction.

During the study, dose escalation will depend on evaluations of safety in cycle 1 of therapy. The following dose escalation rules will be employed:

- Three subjects will be studied at the first dose level. If none of these three subjects experience DLT during cycle 1, then the dose will be escalated to the next higher level in the three subsequent subjects.
- If one of three subjects experiences DLT at the current dose during cycle 1, then three more subjects will be accrued at the same dose. If none of these three additional subjects experience DLT during cycle 1, then the dose will be escalated in subsequent subjects. If one or more of the three additional subjects experiences DLT in the first cycle, the MTD has been exceeded and three more subjects will be treated at the next lower dose (if only three subjects were previously treated at that prior dose).
- If two or more subjects experience DLT in the first cycle, then the MTD has been exceeded and three more subjects will be treated at the next lower dose level (if only three subjects were previously treated at that prior dose).
- No intrasubject dose escalations in subsequent cycles of therapy will be permitted.

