If a subject experiences a DLT during the 28-day course of PTC299 therapy, then study drug administration can be omitted, as necessary, until the adverse event resolves or stabilizes to an acceptable degree (i.e., to < Grade 2). Thereafter, the dose of PTC299 for the remainder of the treatment course during that cycle should be reduced by one dose level; reduction to Dose Level -1 (20 mg/dose BID) may be made for subjects experiencing PTC299-related DLT at Dose Level 1 (40 mg/dose BID); and reduction to Dose Level 4 (100 mg/dose BID) may be made for subjects experiencing PTC299-related DLT at Dose Level 5 (120 mg/dose TID) and reduction to Dose Level 6 (160 mg/dose TID) may be made for subjects experiencing PTC299-related DLT at Dose Level 7 (200 mg/dose TID). Doses during missed days of treatment should not be made up (e.g., if a subject experiences an AE on Day 7 of the treatment course and the event lasts for 3 days, the reduced dose should be administered only for a further 18 days so that the total treatment course duration remains 28 days).

A new cycle of PTC299 treatment may begin when AEs or laboratory abnormalities have returned to baseline levels. If AEs or laboratory abnormalities are not resolved to baseline, week-by-week delays in initiating the new cycle of treatment should be instituted. If it takes longer than 4 weeks for the AE to resolve to baseline, protocol treatment will be permanently discontinued. Once all toxicities have returned to baseline, the next cycle of therapy can be initiated.

Subjects experiencing any of the DLTs described in Section 5.3.3 in the current cycle of therapy should have the dose in the next cycle of therapy reduced by 1 dose level; reduction to Dose Level -1 (20 mg/dose BID) may be made for subjects experiencing PTC299-related DLT at Dose Level 1; reduction to Dose Level 4 (100 mg/dose BID) may be made for subjects experiencing PTC299-related DLT at Dose Level 5 (120 mg/dose TID) and reduction to Dose Level 6 (120 mg/dose TID) may be made for subjects experiencing PTC-related DLT at Dose Level 7 (160 mg/dose TID).

In general, after a dose is reduced for PTC299-related toxicity it should not be re-escalated, even if there is minimal or no toxicity with the reduced dose. However, if further evaluation reveals that the adverse event that led to the dose reduction was not study drug-related, the dose may be re-escalated to the original dose level.

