When there is a dose modification, the subject should be notified of the change in dose and the appropriate clinic staff should instruct the subject about the revised number of study medication capsules to be used per dose according to the new dose level.

Clinical use of other anti-VEGF compounds (e.g., bevacizumab) can be associated with delayed wound healing. For this reason, subjects who require surgery or a deep invasive procedure should have PTC299 held for  $\geq 2$  weeks before the procedure, if possible, and PTC299 should be held for  $\geq 2$  weeks after the procedure, or until complete wound healing, to avoid the theoretical risk of impaired wound closure.

#### 5.3.5 Treatment in Phase 2

Once the safety profile at each dose level has been established based on first cycle DLTs in Phase 1, up to 21 additional subjects whose response to treatment can be evaluated will be enrolled in the Phase 2 portion of the study at the highest safely tolerated dose established in the Phase 1 portion to better define the safety, antitumor activity and biological activities of PTC299 at this dose level. In the Phase 2 portion of the study, Simon's 2-stage design will be used, as described in Section 11.1. Treatment will consist of 4 week cycles of therapy (56 or 84 doses) as described in Section 5.3.2. The maximum duration of treatment is 12, 4-week cycles. Definitions of DLT will be as described in Section 5.3.3. Study drug interruptions and dosage reductions will be managed as described in Sections 5.3.1 and 5.3.4.

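### Dose Levels 3 and 4 are the same dose, so reducing by one level after a DLT leaves a Level 4 subject on 100 mg BID

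*Combined protocol and SAP*

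**What the plan says.** Section 5.3.2 lists the Stage 1 levels, including "Dose Level 2 (80 mg/dose BID), or Dose Level 3 (100 mg/dose BID". For Stage 3 it adds a lower rung: "Dose Level 4 (100 mg/dose BID) is provided in case a subject assigned to dose Level 5 (120 mg/dose TID) requires dose reduction". Section 5.3.6 turns the levels into capsules and gives these two the same count: "five 20-mg capsules per dose will be administered to subjects at Dose Level 3 and 4".

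Section 5.3.4 states the reduction rule twice. Within the cycle, "the dose of PTC299 for the remainder of the treatment course during that cycle should be reduced by one dose level". For the following cycle, subjects with a DLT "should have the dose in the next cycle of therapy reduced by 1 dose level". Both paragraphs name destinations for Levels 1, 5 and 7 only, and Section 5.3.2 also points Level 6 to Level 5. No section names a destination for Level 4 or orders discontinuation for a DLT there. Staff are then to tell the subject "the revised number of study medication capsules to be used per dose according to the new dose level".

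Two labels conflict with these definitions. The next-cycle paragraph of Section 5.3.4 says "reduction to Dose Level 6 (120 mg/dose TID) may be made for subjects experiencing PTC-related DLT at Dose Level 7 (160 mg/dose TID", and Section 5.3.2 says that "8 subjects were enrolled at the Stage 1 MTD, Dose Level 2 (100 mg/dose BID".

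**The concern.** The reduction rule works through level numbers, so it lowers the dose only if each level number stands for a different dose. Levels 3 and 4 do not. Read as written, a subject on Level 4 who has a DLT resumes the dose that caused it.

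Level 4 is where this matters most. Section 5.3.2 provides it for subjects who could not stay on 120 mg TID, so the rule fails in people who have already shown intolerance. Section 3.3.1 also allows a Stage 3 cohort at 100 mg BID, but only after both 160 and 120 mg TID have proved intolerable. For Phase 2, Section 5.3.5 refers reductions to Sections 5.3.1 and 5.3.4. Section 5.3.1 contains no reduction rule, so Section 5.3.4 is the only source.

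The mislabelled Levels 6 and 7 are a separate fault in the same rule, and they reach the main planned cohort. Section 3.3.1 foresees 15 subjects at 200 mg TID if that dose is tolerated. Two sites could give such a subject different next-cycle doses, each with support in the text.

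**Working it through.** **Inputs.** Capsule strength is 20 mg (Section 5.1.1). Capsules per dose for Levels 1 to 7 come from Section 5.3.6. Level -1 (20 mg BID, one capsule) and the BID or TID schedules come from Section 5.3.2.

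**Plan's own figure.** Five capsules × 20 mg = 100 mg per dose at Levels 3 and 4, which agrees with Section 5.3.2. For every level, capsules × 20 mg reproduces the stated mg per dose. Section 5.3.4 also gives Level 4 as 100 mg BID, so the duplicate is not a misprint in one place.

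**Size of each step.** Daily dose = capsules × 20 mg × doses per day. Cut = (current − next lower) / current.

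| Level | Daily dose (mg) | One level down (mg) | Cut |
|---|---|---|---|
| 7 | 10 × 20 × 3 = 600 | 480 | 120/600 = 20% |
| 6 | 8 × 20 × 3 = 480 | 360 | 120/480 = 25% |
| 5 | 6 × 20 × 3 = 360 | 200 | 160/360 = 44.4% |
| 4 | 5 × 20 × 2 = 200 | 200 | 0/200 = 0% |
| 3 | 5 × 20 × 2 = 200 | 160 | 40/200 = 20% |
| 2 | 4 × 20 × 2 = 160 | 80 | 80/160 = 50% |
| 1 | 2 × 20 × 2 = 80 | 40 | 40/80 = 50% |
| -1 | 1 × 20 × 2 = 40 | none | – |

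Level 4 is the only level at which the rule leaves the dose unchanged.

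**Who can be on Level 4.**

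- Subjects reduced from 120 mg TID. A subject who starts at Level 5 meets the gap at the second DLT, at Level 6 at the third, and at Level 7 at the fourth. The documents give no rate from which to count these subjects.
- The Stage 3 fallback cohort of 9 to 15 at 100 mg BID (Section 3.3.1), if it opens and is treated as Level 4. Section 3.3.1 gives it no level number. The documents give no DLT rate, so I assume 10% to 30%. The expected number with a DLT is then 9 × 0.10 = 0.9 to 15 × 0.30 = 4.5. The chance of at least one is 1 − 0.9^9 = 0.61 to 1 − 0.7^15 = 0.995. Both ranges are conditional on that cohort opening.

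**Next-cycle conflict.** A subject on 200 mg TID takes 600 mg/day. By the definition of Level 6, the next-cycle dose is 160 × 3 = 480 mg/day, a cut of 120/600 = 20%. By the dose printed in the next-cycle rule, it is 120 × 3 = 360 mg/day, a cut of 240/600 = 40%.

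**After the fix.** If 100 mg BID steps to 80 mg BID, the cut is (200 − 160)/200 = 20%, the same as the existing step from Level 3 to Level 2.

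**The case against.** The strongest reply is that the rule tells the site to reduce the dose, and going from 100 mg BID to 100 mg BID reduces nothing. The instruction about a revised capsule count also assumes a change. On that view Level 4 is only the Stage 3 name for the Stage 1 dose, and a sensible investigator would go to 80 mg BID or ask. This is probably what was intended, but the text does not say it. A rule for dosing after toxicity should not depend on each site inferring the same thing.

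The narrow reach stands. Reaching Level 4 by individual reduction takes at least one DLT, and a further one is needed to meet the gap. The fallback cohort opens only if two higher doses fail. If that cohort is treated as Level 3, its step is a real 20% cut and it is unaffected.

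There are also other safeguards. Drug can be held until the event settles. A new cycle waits for return to baseline, and treatment stops if that takes more than 4 weeks. Confirmed liver DLTs go to the medical monitors. The Schema and Section 7.0 allow discontinuation for toxicity. These limit the harm, but none of them sets a lower dose.

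Finally, the mislabelled Levels 6 and 7 do not prove the Level 4 point. Both readings of that text lower the dose, and the same-cycle rule with Sections 5.3.2 and 5.3.6 shows what was meant. It is a separate error that the same table corrects.

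**Conclusion.** The concern holds. As written, reducing by one level takes a Level 4 subject from 200 to 200 mg/day, and nothing in the protocol overrides this. That conclusion rests only on the stated doses and needs no assumption. The 0.9 to 4.5 subjects do rest on assumptions: that the fallback cohort opens, that it counts as Level 4, and that its DLT rate is 10% to 30%. The next-cycle rule is also wrong as printed, giving 480 or 360 mg/day for a subject on 200 mg TID. The label in Section 5.3.2 that puts 100 mg BID at Level 2 is a slip for Level 3, and the mg dose beside it is clear.

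This should be fixed because it governs dosing after toxicity. It does not change the MTD definition, the escalation probabilities, the Simon rule, the sample size, the response endpoint or the Section 11.2 summaries of actual dose.

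**What to change.** Give each level number one dose. In Section 5.3.4, replace the two level-based paragraphs with one table in mg and schedule that applies to both the current and the next cycle:

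| Dose at DLT | Reduced dose |
|---|---|
| 200 mg TID | 160 mg TID |
| 160 mg TID | 120 mg TID |
| 120 mg TID | 100 mg BID |
| 100 mg BID, however labelled | 80 mg BID |
| 80 mg BID | 40 mg BID |
| 40 mg BID | 20 mg BID |

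The medical monitors should confirm the 100 to 80 mg BID row, because the protocol names no step below Level 4. Wherever level numbers remain, correct the next-cycle text to Level 6 = 160 mg TID and Level 7 = 200 mg TID, and correct the Stage 2 label in Section 5.3.2 to Level 3.

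The cost is protocol wording and one table, with no extra patients, visits or procedures.

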#### 5.4 Concomitant Medication

In general, concomitant medications and therapies deemed necessary for the supportive care and safety of the subject are allowed, provided their use is documented in the subject records and on the appropriate CRF. Specific exceptions include warfarin, heparin and antiplatelet agents. Use of aspirin or nonsteroidal anti-inflammatory drugs (NSAIDs) at doses not to exceed the maximum recommended dose is permitted.

The administration of any other therapies intended to treat KS including chemotherapy and biologic agents is NOT permitted. The use of other concurrent investigational drugs is not allowed.

##### Antiemetics

Prophylactic treatment with antiemetics is not allowed on the first day of treatment in cycle 1, but can be administered on subsequent treatment days and in subsequent cycles, based on the judgment of the treating physician. At the occurrence of nausea or vomiting of severity grade  $\geq 1$ , it is suggested that the subject receive a 5HT3 blocker such as:

- Ondansetron hydrochloride (Zofran®) 8 mg orally up to 1 hour before PTC299 dosing and up to 2 additional times daily, or
- Granisetron hydrochloride (Kytril®) 1 mg orally up to 1 hour before PTC299 dosing, and 1 mg 12 hours later as needed on the day of dosing.

In the presence of recurring unacceptable nausea or vomiting, the investigator may consider additional medications. Possible agents include:

- Lorazepam (Ativan®) 1 to 2 mg orally every 4 hours.

Nausea and vomiting requiring IV antiemetics should be considered a DLT (see Section 5.3.3).

### Other Concomitant Medications

To the extent possible, administration of any prescription or over-the-counter drug products other than study medication should be minimized during the study period. It is expected, however, that subjects will be receiving antiretroviral therapy for their HIV infection, and may be receiving other drugs to prevent OIs; these are specifically allowed, as discussed in Section 5.4.1. Subjects should be discouraged from use of street drugs, health foods, herbal remedies, self-prescribed drugs, tobacco products, or excessive alcohol at any time during clinical studies of PTC299.

If considered necessary for the subject's well being, drugs for concomitant medical conditions or for symptom management may be given at the discretion of the investigator. The decision to authorize the use of any drug other than study medication should take into account subject safety, the medical need, the potential for drug interactions, the possibility for masking symptoms of a more significant underlying event, and whether use of the drug will compromise the outcome or integrity of the study.

Because it is possible that PTC299 may slow the clearance of drugs that are primarily metabolized by CYP2D6, investigators should pay specific attention to use of drugs that are known substrates of this enzyme, particularly when such drugs may have a low therapeutic index. Concomitantly administered substrates for CYP2D6 that may require special attention include certain chemotherapeutic drugs (anthracyclines and vinca alkaloids) most antidepressants (tricyclic antidepressants, selective serotonin reuptake inhibitors, and others), many antipsychotics, many beta-adrenergic receptor blockers, and certain anti-arrhythmics. In addition, several antiretroviral agents, including ritonavir, lopinavir/ritonavir, and delavirdine, rely to some extent on CYP2D6 for their clearance.

Subjects should be instructed about the importance of the need to inform the clinic staff of the use of any drugs or remedies (whether prescribed, over-the-counter, or illicit) before and during the course of the study. Any concomitant drugs taken by a subject during the course of the study and the reason for use will be recorded on the CRFs.

#### 5.4.1 Permitted Medications

- Antiretroviral therapy for HIV infection
- Treatment, maintenance or chemoprophylaxis with approved agents for opportunistic infections as clinically indicated
- Topical and/or oral antifungal agents
- Antibiotics as clinically indicated
- Erythropoietin is permitted at the discretion of the Investigator
- Granulocyte colony stimulating factors as clinically indicated for > grade 3 neutropenia at the discretion of the Investigator.
- Regularly prescribed medications such as antipyretics, analgesics, allergy medications, antidepressants, sleep medications, oral contraceptives, megestrol acetate, testosterone or any other medications are permitted except for prohibited medications (see Section 5.4.2).

- Alternative therapies such as vitamins not exceeding the recommended daily allowance, acupuncture and visualization techniques will be permitted. Subjects should report the use of these therapies and they will be recorded.
- Use of aspirin or nonsteroidal anti-inflammatory drugs (NSAIDs) at doses not to exceed the maximum recommended dose is permitted.

#### 5.4.2 Prohibited Medications

- Investigational drugs with the exception of antiretroviral agents that are being obtained through an expanded access protocol.
- Warfarin at any dose.
- Heparins, including low molecular weight heparins.
- Antiplatelet agents (e.g., clopidogrel bisulfate)
- Systemic cytotoxic chemotherapy or any other treatment specifically prescribed to treat KS (e.g., radiation, etc.).
- Routine use of systemic corticosteroid therapy other than replacement doses is not permitted.

#### 5.4.3 Diet

- There are no specific dietary restrictions in the study. PTC299 may be taken with or without food.

### 5.5 Treatment Compliance

Records of study medication used, dosages administered, and intervals between visits will be kept during the study. Drug accountability will be noted at the completion of the trial. Subjects will be asked to return all unused medication at the monthly visits.

Subjects will also be given a diary to carry home and will be instructed to record each time study drug is administered. The subject will be asked to bring the diary to each clinic visit (see Appendix XI).

## 6.0 REPORTING OF ADVERSE EVENTS

This study will utilize the Common Terminology Criteria for Adverse Events (CTCAE) Version 3.0 for reporting. A copy of the CTCAE version 3.0 can be downloaded from the CTEP home page (<http://ctep.info.nih.gov>). All appropriate treatment areas should have access to a copy of the CTCAE version 3.0. The document “CTEP, NCI Guidelines: Adverse Event Reporting Requirements” clearly outlines reporting criteria and can be downloaded from the CTEP web site (<http://ctep.cancer.gov/reporting/adeers.html>).

This study will be monitored by the Clinical Data System (CDS). Cumulative CDS data will be submitted quarterly to CTEP by electronic means. Reports are due January 31, April 30, July 31, and October 31.

### 6.1 Classification of AEs by Severity and Relationship to Study Drug Administration

#### Adverse Event

Any unfavorable and unintended sign (including an abnormal laboratory finding), symptom or disease temporally associated with the use of a medical treatment or procedure regardless of whether it is considered related to the medical treatment or procedure (attribution of unrelated, unlikely, possible, probable, or definite).

#### Life-Threatening Adverse Event

Any AE that places the subject or subject in view of the Investigator, at immediate risk of death from the reaction.

#### Serious Adverse Event (SAE)

Any AE occurring at any dose that results in any of the following outcomes: Death, a life-threatening AE, inpatient hospitalization or prolongation of existing hospitalization, a persistent or significant disability/incapacity, or a congenital anomaly/birth defect.

Please note for hospitalization – All hospitalizations (or prolongation of existing hospitalization) for medical events equivalent to CTCAE Grade 3, 4, 5 must be reported regardless of the requirements for the phase of study, expected or unexpected, and attribution. For example, do not report an admission for pharmacokinetic sampling, but do report an admission for a myocardial infarction.

#### Toxicity

Toxicity is a term NOT clearly defined by regulatory organizations. Toxicity has been described as an AE that has an attribution of possibly, probably or definitely related to investigational treatment. To minimize confusion the NCI would recommend that the term toxicity NOT be utilized for AE reporting purposes. The CTCAE continues to use the term ‘toxicity’ because of familiarity.

### Unexpected Adverse Event

Any AE that is not listed in available sources including the package insert, the Investigator's Brochure, or the protocol.

